2.6 Analysis of the key secondary objective

Not Applicable.

2.7 Analysis of secondary efficacy objective(s)

The secondary efficacy objectives are to:

- Evaluate ORR by investigator assessment per RANO
- Evaluate duration of response (DOR) by investigator and central independent review per RANO
- Evaluate progression-free (PFS) survival by investigators and central independent review assessment per RANO
- Evaluate time to response (TTR) by investigators and central independent review assessment per RANO
- Evaluate CBR by investigators and central independent review assessment per RANO
- Evaluate overall survival (OS)

2.7.1 Secondary endpoints

ORR by investigator assessment

The evaluation of ORR will be repeated by investigator assessment as per RANO criteria based on the FAS and the Evaluable Set separately. ORR will be summarized using descriptive statistics (N, %) along with 2-sided exact 95% and 80% CIs [Clopper CJ and Pearson ES. (1934)

The use of confidence or fiducial limits illustrated in the case of the binomial. Biometrical, 26, 404-413].

Duration of response

DOR only applies to patients whose BOR is CR or PR according to RANO criteria. The start date is the date of first documented response of CR or PR (i.e., the start date of response, not the date when response was confirmed), and the end date is defined as the date of the first documented progression per RANO or death due to any cause. If a patient has not progressed or died or has received any further anticancer therapy at the analysis cut-off date, DOR will be censored at the date of the last adequate tumor evaluation date before the cut-off date or before the start of the new anticancer therapy date, whichever is earlier (see Section 2.7.3).

DOR will be analyzed as per investigator and central independent review separately. The analyses of DOR will be based on the FAS and will be repeated based on the evaluable set.

Progression-free survival

PFS is defined as the time from the start date of study treatment to the date of the first documented progression or death due to any cause. PFS will be calculated using RANO criteria based on investigator and central independent review of tumor assessments separately. The analysis will include all data observed up-to the cut-off date. If a patient has not progressed or died or has received any further anticancer therapy at the analysis cut-off date, PFS will be censored at the date of the last adequate tumor evaluation date before the cut-off date or before the start of the new anticancer therapy date, whichever is earlier. (See Section 2.7.3 for additional details regarding censoring rules and determination of date of last adequate tumor assessment). Discontinuation due to disease progression (collected on the 'End of treatment' and 'End of post treatment follow up' disposition pages) without supporting evidence satisfying progression criteria per RANO will not be considered disease progression for PFS derivation. The analysis will be based on FAS and Evaluable Set separately.

Time to response

Time to response (TTR) of CR or PR is the time from start date of study treatment to first documented response of CR or PR (which must be confirmed subsequently) according to RANO criteria. All patients in the FAS will be included in the TTR calculation. Patients who did not achieve a confirmed PR or CR will be censored at:

- the maximum follow-up time (i.e. FPFV LPLV used for the analysis) for patients who had a PFS event (i.e. either progressed or died due to any cause);
- the last adequate tumor assessment date for all other patients.

TTR will be analyzed using investigator and independent reviewer assessments separately.

Clinical Benefit Rate

CBR is defined as the proportion of patients with a BOR of CR or PR, or an overall lesion response of SD which lasts for a minimum duration of 24 weeks. A patient will be considered to have SD for 24 weeks or longer if a SD response is recorded at 23 weeks or later (i.e. \geq 161 days) from treatment start date, allowing for the \pm 1 week visit window for tumor assessments.

CBR will be analyzed using investigator and independent reviewer assessments separately. CBR will be calculated using the FAS set and Evaluable Set separately.

Overall Survival

OS is defined as the time from start date of study treatment to date of death due to any cause.

If a patient is not known to have died at the time of analysis cut-off, OS will be censored at the date of last contact (Section 2.1.1).

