1.1 Study design

This study combines two pediatric glioma cohorts (HGG and LGG) into a single multi-center, open-label, phase II study.

The HGG cohort is a multi-center, single-arm, open-label, Phase II study conducted in children and adolescent patients with BRAF mutation positive, refractory or relapsed HGG tumors after having received at least one previous standard therapy. BRAF V600 mutation-positive tumor was assessed locally, or at a Novartis designated central reference laboratory if local BRAF V600 testing was unavailable. Approximately 40 patients will be enrolled to receive dabrafenib and trametinib.

The primary objective is to evaluate the antitumor activity of dabrafenib in combination with trametinib, as measured by the overall response rate (ORR) to study treatment by independent central review assessment using response assessment in neuro-oncology (RANO) criteria in the Full Analysis Set (FAS) population. ORR as assessed through investigator review, duration of response (DOR), time to response (TTR), progression-free survival (PFS), clinical benefit rate (CBR) assessed by investigator and independent central review, overall survival (OS), palatability, pharmacokinetics (PK), and the safety and tolerability profile of dabrafenib and trametinib are secondary endpoints.

Patients may continue to receive the assigned study treatment until disease progression by RANO criteria or loss of clinical benefit as determined by the investigator, unacceptable toxicity, start of a new anti-neoplastic therapy, discontinuation at the discretion of the investigator or patient/legal guardian, lost to follow-up, death, or study is terminated by the sponsor.

Patients who have disease progression by RANO criteria may continue study treatment if the investigator determines that patient has clear evidence of clinical benefit from study treatment, continuing study treatment may be in the best interest for the patient, and the patient/legal guardian is willing to continue on study treatment and sign the informed consent for treatment beyond progression. The decision to continue study treatment after progressive disease (PD) must be documented in the patient records and electronic case report forms (eCRF) after every tumor evaluation. In this case, the patient will continue assessments as defined in the study

Novartis	Confidential	Page 8
SAP Final Analysis HGG		CDRB436G2201

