[Protocol Section 7]. An end of treatment visit will be performed when patients permanently discontinue study treatment.

Patients who discontinue the study treatment without disease progression by RANO criteria will continue tumor assessments as outlined in the study protocol section 7 until documented centrally confirmed disease progression by RANO criteria or death irrespective of start of new anti-neoplastic therapy.

Patients who discontinue study treatment and efficacy follow-up will enter a follow-up period during which survival will be collected every 3 months. During the survival follow-up, subsequent anti-neoplastic therapies initiated after study treatment discontinuation will be collected.

The final analysis will be performed when all patients in both cohorts have been followed for survival for at least 2 years from last patient first study treatment, except if consent is withdrawn, death, or patient is lost to follow-up or study discontinuation.

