2.5 Analysis of the primary objective

The primary objective is to demonstrate the antitumor activity of dabrafenib in combination with trametinib as measured by ORR to study treatment by central independent review assessment using RANO criteria, in children and adolescent patients with BRAF V600 mutation positive relapsed or refractory HGG.

2.5.1 **Primary endpoint**

ORR is defined as the proportion of patients with best overall response (BOR) of confirmed complete response (CR) or partial response (PR) according to RANO criteria (see Appendix 3 of the study protocol). ORR will be calculated based on the FAS using central independent review of tumor assessment data. Only tumor assessments performed before the start of any further antineoplastic therapy (i.e. any additional secondary antineoplastic therapy or surgery) will be considered in the assessment of BOR. See Section 5.6 for primary estimand definition.

Best overall response

The BOR will be assessed based on reported responses across all evaluation time points. Both CR and PR must be confirmed by repeat assessments performed not less than 4 weeks after the criteria for response are first met. The next scheduled assessment may be used for purposes of

confirmation of response. In the absence of a confirming scan 4 weeks later, this response will be considered only stable disease (SD).

BOR for each patient is determined from the sequence of overall responses according to the following rules, up to progression:

- CR = at least two determinations of CR at least 4 weeks apart before progression
- PR = at least two determinations of PR or better at least 4 weeks apart before progression (and not qualifying for a CR)
- SD = requires at least one SD assessment (or better) determined at or beyond the second regularly scheduled tumor assessment (nominally week 16 i.e >= 105 days allowing for the ±1 week visit window) after start of study treatment (and not qualifying for CR or PR).
- PD = progression after start of study treatment (and not qualifying for CR, PR or SD).
- UNK = all other cases (i.e. not qualifying for confirmed CR or PR and without SD at or beyond the second regularly scheduled post-baseline tumor assessment or progression)

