If a patient receives any further anti-neoplastic therapy while on study, any subsequent assessments will be excluded from the BOR determination. Further anti-neoplastic therapies will be identified via protocol deviations or from the data collected on 'Anti-neoplastic therapies since last date of study drug' as appropriate.

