2.13 Crossover Phase

Baseline

Baseline is defined as the most recent non-missing value before the first dose of study treatment (dabrafenib plus trametinib) on the crossover treatment period. Baseline values will be established prior to the start of the crossover phase.

Response will be determined separately for the randomized phase and the crossover phase. Baseline lesion assessments will be re-established prior to initiation of crossover therapy and response will be calculated based on the appropriate baseline for each respective phase.

On-treatment assessment/event and observation periods

For AE reporting the overall observation period will be divided into three mutually exclusive segments:

- 1. *pre-treatment period*: up to 90 days prior to the first dose on the crossover phase
- 2. *on-treatment period*: from date of first administration of crossover study treatment to 30 days after date of last actual administration of study treatment (including start and stop date)
- 3. *post-treatment period*: starting at day 30+1 after last administration of crossover study treatment.

The reference date for both efficacy and safety measures in the Crossover phase is the date of first dose of dabrafenib or trametinib on the crossover treatment period.

The tables and listings for the randomized and crossover phases will be separate. Note: Analyses specified as for the Randomized phase will only include data prior to crossover except for analyses of OS. Similarly analyses specified for the crossover phase will only use data from after the date of crossover.

Only key summary tables will be provided for the crossover phase for example; disposition, treatment discontinuation, exposure, deaths, AE/SAEs, ORR, and time to response. Listings will be provided for the crossover data.

3 Sample size calculation

The sample size calculation was based on the primary analysis and is not applicable for the final analysis.

4 Change to protocol specified analyses

No change from protocol specified analysis was made.

5 Appendix

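### The 24-week stable-disease rule for CBR lacks the progression and new-therapy limits that BOR, DOR and PFS carry, so stable disease recorded after either event can count as clinical benefit

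*SAP*

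**What the plan says.** The definition in the HGG final SAP, section 2.7.1, counts a BOR of CR or PR, "or an overall lesion response of SD which lasts for a minimum duration of 24 weeks". The next sentence makes this operational: "A patient will be considered to have SD for 24 weeks or longer if a SD response is recorded at 23 weeks or later", given as at least 161 days from treatment start. The LGG final SAP, section 2.7.1, has the same rule counted from randomization. CBR is derived separately for investigator and central review.

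The related endpoints are bounded:

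- **BOR, progression** (section 2.5.1): "BOR for each patient is determined from the sequence of overall responses according to the following rules, up to progression".
- **BOR, new therapy** (section 2.5.1): once further anti-neoplastic therapy starts, "any subsequent assessments will be excluded from the BOR determination".
- **BOR of SD** (section 2.5.1): "requires at least one SD assessment (or better) determined at or beyond the second regularly scheduled tumor assessment". The same section treats a CR or PR without a confirming scan as SD.
- **DOR and PFS** (section 2.7.3): these end at first progression or death, and are censored at the last adequate assessment when new therapy comes first.

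Section 2.7.3 of the LGG final SAP also counts unknown or missing BOR as non-response for CBR. The HGG final SAP has no CBR paragraph there. Its rule that unknown BOR is a failure (sections 2.5.2 and 5.6.2) is written for ORR.

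**The concern.** The SD part of CBR uses the visit-level overall lesion response, not BOR, so the BOR limits do not carry over by themselves. The sentence that would be programmed needs one SD reading on or after day 161 and has no upper limit.

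Readings after progression or after a switch can exist in this trial. Section 1.1 says "Patients who have disease progression by RANO criteria may continue study treatment if the investigator determines" certain conditions, with assessments continuing. In the RANO summary table (Table 5-7) worsened clinical status alone is enough for PD, so a later SD reading is possible. Patients who stop treatment without RANO progression are scanned "until documented centrally confirmed disease progression by RANO criteria or death irrespective of start of new anti-neoplastic therapy". Because that stopping point is central confirmation, investigator SD readings can also follow an investigator PD that central review did not confirm.

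CBR could then credit the study treatment with disease control seen after it had failed or while another drug was being given. One patient could appear as BOR = PD and as a clinical benefit in the same report.

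**Working it through.** **1. The plan's threshold.** 23 weeks × 7 = 161 days, which matches section 2.7.1.

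**2. The plan's interval method.** CBR uses exact (Clopper-Pearson) 95% limits. Recomputing rows of Table 3-1 in the HGG SAP Amendment 2 gives 14/40: 20.6 to 51.7; 18/40: 29.3 to 61.5; 20/40: 33.8 to 66.2. All three match.

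**3. The rule applied to illustrative patients.** These sequences are invented to test the wording. The last column is the rule with SD or better required on or after day 161, before progression and before new therapy.

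| Sequence | Literal rule | Literal rule, unconfirmed CR/PR counted as SD | Bounded rule |
|---|---|---|---|
| A. PD at weeks 8 and 16, treated beyond progression, SD at day 161 | benefit | benefit | no benefit |
| B. SD at weeks 8 and 16, new therapy, SD at day 161 | benefit | benefit | no benefit |
| C. SD at weeks 8 and 16, unconfirmed PR at day 161, PD at week 32 | no benefit | benefit | benefit |
| D. SD through day 161, then PD | benefit | benefit | benefit |

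- **A** has BOR = PD. The LGG unknown-BOR line does not catch it, so it is a CBR success in both cohorts.
- **B** has BOR = SD, from the week-16 reading (day 105 or later). The LGG line does not catch it either.
- **Early switch.** Take SD at week 8 only, a new therapy at week 10, and SD at day 161. Assessments after the switch are excluded from BOR, and SD only before week 16 makes BOR unknown. The LGG SAP therefore classes this patient as a CBR non-responder. The HGG SAP has no such line, so the literal rule gives benefit.

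**4. Size per patient.**

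- HGG: about 40 patients, 1/40 = 2.5 points.
- LGG: about 102 patients at 2:1, i.e. 102 × 2/3 = 68 and 102 × 1/3 = 34. Then 1/68 = 1.5 points and 1/34 = 2.9 points.

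**5. Effect on an HGG estimate.** Assume a true count of 20/40 for illustration; neither this nor the number affected is in the documents.

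| Extra patients counted | CBR | Exact 95% CI |
|---|---|---|
| 0 | 50.0% | 33.8 to 66.2 |
| 1 | 52.5% | 36.1 to 68.5 |
| 2 | 55.0% | 38.5 to 70.7 |
| 4 | 60.0% | 43.3 to 75.1 |

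**The case against.** The best defence is that the definition requires stable disease to last 24 weeks. Stable disease interrupted by PD has not lasted, and the following sentence may be meant only to set the day and the visit window. The text is silent on readings after PD or new therapy; it does not expressly admit them. Scoring of SD after PD may also be governed by protocol Appendix 3, which is not available here. This shows the likely intent. It does not repair the sentence, which says when the 24-week condition is met and needs only one reading. The word lasts also does not deal with new therapy, since SD can continue unbroken across a switch.

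It is also true that CBR is descriptive, that PFS at 6 months with explicit limits is reported alongside it, and that all response data are listed. These points limit the consequences.

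Three stronger readings are tempting, but the documents do not support them:

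- **Readings better than SD are ignored, so CBR is also understated.** Confirmed CR and PR count through BOR, and section 2.5.1 treats an unconfirmed CR or PR as SD, which classes sequence C correctly. What remains is an ambiguity: the downgrade sits in the BOR section, and the CBR sentence omits the phrase that admits better readings.
- **The LGG comparison is biased towards dabrafenib plus trametinib.** One might infer this because that arm can be treated past PD while, for controls who cross over, "Analyses specified as for the Randomized phase will only include data prior to crossover except for analyses of OS". But crossover is elective, and scans after a new therapy can occur in either arm. The LGG SAP plans rates and an odds ratio for CBR, not a difference, and no net direction can be derived.
- **Every early switcher counts as a benefit.** In LGG the unknown-BOR line prevents this.

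**Conclusion.** The point holds as an error in a stated rule. Programmed as written, SD on or after day 161 that follows RANO progression counts as clinical benefit in both cohorts. SD after a new therapy counts in HGG, and in LGG when BOR is not unknown. This contradicts the 24-week duration in the definition and the limits used for BOR, DOR and PFS. It also means that the two final SAPs classify the same early switcher differently.

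The definite error is upward: 2.5 points per affected patient in HGG, 1.5 in LGG dabrafenib plus trametinib and 2.9 in LGG control, assuming the planned numbers of 40, 68 and 34. The documents do not say how many patients are affected, so the total is unknown and could be zero. No test, alpha or sample size depends on it. The change is worth making because the estimate and the LGG odds ratio will be reported and the correction is simple.

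**What to change.** In section 2.7.1 of both final SAPs, keep the 161-day threshold and state that the qualifying overall response must be:

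- SD or better, with an unconfirmed CR or PR counted as SD as in section 2.5.1;
- recorded before the first RANO progression by the same assessor; and
- recorded before any further anti-neoplastic therapy, using the truncation already defined for BOR.

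Add to section 2.7.3 of the HGG final SAP the LGG line that counts unknown or missing BOR as non-response for CBR.

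Section 2.7.1 of the primary-analysis SAPs (LGG Amendment 1 and HGG Amendment 2) has the same unrestricted sentence. The final report should therefore say that the definition was tightened after the primary analysis.

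The cost is a short text change in each SAP and re-use of the BOR truncation. CBR may fall slightly and may differ from the primary-analysis figure for reasons other than longer follow-up.

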OS will be described in tabular and graphical format using Kaplan-Meier methods as described for DOR, including estimated median (in months) with 95% CI [Baumgartner RN, Roche AF, Himes (1986). Incremental growth tables: supplementary to previously published charts. American Journal of Clinical Nutrition, 43, 711-22.

Brookmeyer R and Crowley J. (1982)], 25th and 75th percentiles and Kaplan-Meier estimated probabilities with corresponding 95% CIs at timepoints up to the maximum follow-up (including at least 6, 12, 18 and 24 months).

2.7.3 Handling of missing values/censoring/discontinuations

DOR and PFS

If a patient has not progressed or is not known to have died at the date of analysis cut-off or has received any further anticancer therapy, DOR and PFS will be censored at the date of the last adequate tumor before the cut-off date or before the start of the new anticancer therapy date, whichever is earlier.

The date of last adequate tumor assessment is the date of the last tumor assessment with overall lesion response of CR, PR or SD before an event or a censoring reason occurred. In this case the last tumor evaluation date at that assessment will be used. If no post-baseline assessments are available (before an event or a censoring reason occurred) then the start date of treatment will be used.

In particular, DOR and PFS will be censored at the last adequate tumor assessment if one of the following occurs: absence of event; the event occurred after a new anticancer therapy is administered; the event occurred after two or more missing tumor assessments. The term "missing adequate tumor assessment" is defined as a tumor assessment (TA) not performed or tumor assessment with overall lesion response of "UNK". The rule to determine number of missing TAs is based on the time interval between the date of last adequate tumor assessment and the date of an event. If the interval is greater than twice the protocol-specified interval between the TAs and 2 times the protocol-allowed time window around assessments, then the number of missing assessments will be 2 or more.

Refer to Table 2-9 for censoring and event date options and outcomes for DOR and PFS.

Table 2-9Outcome and event/censor dates for DOR and PFS analysis

Situation	Date	Outcome
No baseline assessment	Date of start of study treatment	Censored
Progression or death at or before next scheduled assessment	Date of progression (or death)	Progressed

Situation	Date	Outcome
Progression or death after exactly one missing assessment	Date of progression (or death)	Progressed
Progression or death after two or more missing assessments	Date of last adequate assessment prior to missed assessment	Censored
No progression (or death) New anticancer therapy (including cancer related surgery and radiotherapy) given prior to protocol defined progression	Date of last adequate assessment Date of last adequate assessment on or prior to starting new anti-cancer therapy	Censored Censored
Death before first PD assessment	Date of death	PFS event

Censoring pattern of PFS

Number of patients with a PFS event and number of patients censored for the PFS analysis will be summarized. In addition, a summary of reasons for PFS censoring will be provided by based on the following reasons:

- 1: Ongoing without event
- 2: Lost to follow-up
- 3: Withdrew consent
- 4: Adequate assessment no longer available
- 5: Initiation of new cancer therapy prior to progression
- 6: Event after >=2 missing tumor assessments

The PFS censoring reasons are defined in the following way.

If the time interval between the last adequate TA date and the earliest of the following dates is smaller or equal to interval of 2 missing tumor assessments (see Section 2.7.3 for definition):

- 1. Analysis cut-off date,
- 2. Start date of further anti-neoplastic therapy,
- 3. Date of consent withdrawal,
- 4. Visit date of study treatment discontinuation or end of post-treatment follow-up discontinuation due to lost to follow-up.

Then the PFS censoring reason will be:

- 1. 'Ongoing',
- 2. 'New cancer therapy added',
- 3. 'Withdrew consent',
- 4. 'Lost to follow-up',

If the time interval is larger than the interval of 2 missing tumor assessments with no event observed, then the PFS censoring reason will always default to 'Adequate assessment no longer available'. If the time interval between the last adequate tumor assessment date and the PFS event date is larger than the interval of 2 missing tumor assessments then the patient will be censored and the censoring reason will be 'Event documented after two or more missing tumor assessments'.

These summaries on censoring reasons will be produced for PFS by investigator and central independent reviewers. The censoring patterns will be compared between investigator and central independent reviewers.

OS

If a patient is not known to have died at the time of analysis cut-off, then OS will be censored at the date of last known date patient was alive, i.e., last contact date (see Section 2.1.1).

